Protocol Title: Oscillatory Positive Expiratory Pressure Devices in Acute Inpatient Treatment of Pneumonia

NCT number: NCT04540510

Version Date: 2/4/2019

Background:

Pneumonia is one of the most common health conditions leading to hospitalization today. Approximately 1.3 million people in the US are admitted to the hospital with community-acquired pneumonia (CAP) annually, with readmission rates within the first 30 days as high as 20%. In a retrospective analysis of patients with culture-confirmed bacterial pneumonia, 30-day readmission occurred in 19.3% of patients. At Norwalk Hospital, the 30-day readmission rate for patients with pneumonia is 13.1%. CAP is the sixth most common cause of death with a case-fatality rate of up to 16% for hospitalized CAP patients, and an overall 30-day mortality up to 23%. The economic burden of CAP is also high, with a CAP cost burden estimated to be at least \$13 billion in 2008 within just the Medicare population.

Antibiotics represent the mainstay of pneumonia treatment with other therapies being mostly supportive. In bacterial CAP, prompt initiation of antibiotic therapy is critical in preventing mortality however the optimal duration of antibiotic therapy in CAP is unknown. Current guidelines recommend antibiotic courses of 7 to 21 days, depending on illness severity and type of pathogen. However, adherence to guidelines is variable and physicians tend to treat longer with antibiotics, especially in elderly patients with comorbidities and patients with severe CAP. Duration of antibiotic therapy can be guided by clinical signs such as defervescence, decrease in sputum production and coughing, or improvement of general condition. There is harm associated with antibiotic usage, however, ranging from development of antibiotic resistance to antibiotic-associated diarrhea to *Clostridium Difficile* infection. Thus, strategies to reduce the duration of antibiotics are clinically important and necessary.

The mucosal lining of the respiratory tract originates from products of secretory cells interspersed among mucosal cells or within submucosal glands, and it protects the underlying mucosa from dehydration. Current understanding is that the lining is a two-fluid model in which the upper layer is a viscoelastic gel (mucus, cross-linked glycoproteins) that overlies a sol layer (serous). Sensory stimuli enhance mucus secretion and cause bronchoconstriction, responses that are usually coupled to cough and two-phase gas–liquid clearance of mucus. During times of inflammation, such as with pneumonia, mucus hypersecretion and mucus layer transport is delayed, and abnormal clearance then predominates in the smaller peripheral airways.

When treating patients with respiratory secretion problems such as pneumonia, it is advantageous to help clear the patient's lungs of the secretions as failure to clear secretions

can lead to obstruction from mucus plugging, sequestration of bacteria, ongoing fever, hypoxemia, and prolonged duration of disease, for instance. These infected secretions are best dislodged by a series of two different therapies which are combined in an oscillatory positive expiratory pressure (oPEP) device. First, a positive expiratory pressure (PEP) is exerted back into the lungs, gently increasing air pressure into the bronchi and pulmonary alveoli. This pressure prevents airway collapse by stenting the airways open, or increasing intrathoracic pressure distal to retained secretions, by collateral ventilation or by increasing functional residual capacity. Second, the application of a series of pressure waves (oscillatory vibrations) additionally provides a percussive effect, reducing the viscoelasticity of the mucus, and dislodging these secretions from the lungs so that they can be expelled. This can be accomplished with an oPEP device that uses the patient's own breathing to generate a series of pressure waves with each exhalation cycle that causes the thorax to vibrate and loosen the mucus so that it may be expelled.

Airway clearance is a strategy for treating symptoms of respiratory disorders by improving a patient's respiratory status by enhancing mucus clearance, reducing airway resistance, enhancing gas exchange, and reducing overall work of breathing. Chest physiotherapy and airway clearance has been the mainstay of treatment and prevention of exacerbation in the cystic fibrosis (CF) population for decades, and has had its use expanded to the non-CF bronchiectasis and acute bronchiolitis populations, and in patients being mechanically ventilated. There have also been recent positive trials within the realm of chronic bronchitis and COPD as well which showed that airway clearance was beneficial in reducing the daily volume of sputum produced and increasing FEV₁.

There have been several small studies done to analyze the utility of airway clearance and its potential role in CAP. These studies have generally been small and have used a wide variety of airway clearance devices and techniques, including external chest wall physiotherapy devices and postural drainage, both now considered second line therapies for most patients. These studies have been variable in their findings and overall have not shown that airway clearance is either beneficial or harmful in CAP. The studies did show, however, that the duration of fever and hospital length of stay were both significantly decreased, suggesting the possibility of other clinically important benefits.(Ntoumenopoulos 2002; Tydeman 1989).

Objectives:

We will test our hypothesis that the use of oPEP devices, specifically the handheld Aerobika (Monaghan Medical) in this study, will result in more rapid and durable recovery in patients hospitalized with community-acquired pneumonia as measured by decreased hospital length of stay, reduced duration of fever, improvement in dyspnea, decreased duration of antibiotics, increased rate of diagnosis of the etiologic organism responsible for the pneumonia, and reduced readmission rates:

Primary outcome

1. Reduction in hospital length of stay

Secondary outcomes

1. Reduction in dyspnea by modified-Borg score
2. Reduction in duration of antibiotics
3. Reduction in duration of fever
4. Reduction in need for oxygen at hospital discharge
5. Reduction in 30-, 60-, and 90-day readmission rates
6. Diagnosis of organism by sputum
7. Transfer to the intensive care unit (ICU)

Study type: Prospective randomized controlled trial**Design:**

The study investigators will perform daily screening by chart review of patients admitted to the hospital in the previous 24 hours using the ICD-10 codes as below to find appropriate patients for secondary screening:

J13 Pneumonia due to Streptococcus pneumoniae

J14 Pneumonia due to Hemophilus influenzae

J15 Bacterial pneumonia, not elsewhere classified

J16 Pneumonia due to other infectious organisms, not elsewhere classified

J17 Pneumonia in diseases classified elsewhere

J18 Pneumonia, unspecified organism

J69 Pneumonitis due to inhalation of food and vomit

A partial HIPAA waiver will be obtained for the purposes of focused screening for eligibility. If the patient is deemed eligible for the study, the study investigators will approach the hospitalist/teaching attending for collateral information and permission to approach the patient for consent. After consent is obtained, the study investigator will perform a brief patient interview to obtain information on race/ethnicity, smoking and alcohol history, to confirm past medical and medication histories, and to perform baseline assessments of dyspnea (modified BORG).

Once consent is obtained, Patients will then be randomized using block randomization. We will receive pre-made envelopes in blocks of 10 from a centralized research coordinator. Investigators performing the initial screening and enrollment will be blinded to the envelope contents until after the patient consents to participation in the study. Once the patient consents to participation, the next consecutively numbered envelope will be opened revealing the allocation to either the control or intervention group. The principal investigator will keep the envelopes secured, and will be responsible for providing each envelope to the enrolling investigator after consent has been obtained.

The intervention will consist of oPEP therapy added to standard pneumonia care (see below). "Standard pneumonia care" will not be dictated by the study protocol, but rather at the discretion of the treating clinicians. Patients who are initially admitted to the intensive care unit (ICU) will not be included in this study even when they are downgraded to general medical floors, but patients will not be excluded if they are enrolled while on the medical floors and are later upgraded to ICU level of care. Enrollment will occur Monday through Friday, thus including patients being admitted on Sunday through Friday.

Patients in the intervention group will be directed to perform the Aerobika therapy twice daily under the guidance of a study investigator for a total of at least 5 minutes per session. The study investigator will appropriately adjust the device on first use, as well as teaching the patient the correct technique for device usage. The primary patient-centered outcome will be the modified-Borg score for dyspnea which will be collected on admission, and on each subsequent morning until discharge on all enrolled patients. Patients will be encouraged to use the device on their own between the monitored sessions, as the device can safely be used multiple times daily. Patients will be surveyed each morning to self-report additional usage of the device. The device will also be available in the patient's room for in-line use of nebulizer treatments

administered by respiratory therapists, at the discretion of the therapist. Ordering of any nebulized medications is at the discretion of the treating clinicians or respiratory therapists, the latter through a standard and general respiratory therapist-driven protocol used in our institution. Charting of any nebulizer therapy will be reviewed to assess additional use of the device as well. The intervention will continue through the duration of the patient's hospitalization, and the patient will have the option to take the device at home with them if they wish to continue using it after discharge. If patients experience intolerable dyspnea or chest tightness during use of the Aerobika, despite coaching and troubleshooting by the bedside investigator, the Aerobika session will be aborted. If the patient is unable to tolerate the therapy during three consecutive sessions, then the patient will be withdrawn from intervention.

Crossover into the Aerobika group will not be restricted if the attending physician treating the patient deems it a necessary part of the patient's care. Rates of crossover will be collected as part of study data. All analyses will be performed using intention-to-treat as well as a modified intention-to-treat method considering the intervention group to include patients randomized to intervention AND who received at least one Aerobika treatment.

Variables to be collected

Demographics: Age at admission Gender Race/ethnicity (self-reported)	Lifestyle: Smoking history (ever/current/never) Alcohol consumption frequency
Home and inpatient medications: PPI/H2-blockers Statins? Hypoglycemics/insulin Systemic steroids Inhaled medications including by nebulization Immunosuppressives	Symptoms:

Physical/Vital signs: BMI (height/weight at admission) Heart rate (daily maximum/minimum) Pulse oximetry (daily maximum/minimum, including FiO2 maximum/minimum) Temperature (daily maximum/minimum) Blood pressure (daily maximum/minimum)	Comorbidities/Past Medical History : CVA Heart disease Renal failure Cancer, active in last 6 months or not (excluding non-melanoma skin cancers) Lung disease (ie. asthma, COPD, ILD, bronchiectasis) GERD Oropharyngeal or other dysphagia
Scores: PSI - pneumonia severity index CURB65 Subjective (cough, dyspnea, mucus production) Modified-Borg score for dyspnea	

Sample size calculations

The median hospital length of stay (LOS) for Norwalk Hospital based on FY2017 data was 4.6 days (SD 3.16 days) for patients coded with a primary diagnosis of pneumonia. We will employ an effect size of 25%, powering for a reduction in LOS by 1 day.

**Two independent study groups
The primary endpoint is an average LOS (continuous variable).**

Sample Size
 Group 1 119
 Group 2 119
 Total 238

Study Parameters
 Mean LOS, group 1 4.6
 Mean LOS, group 2 3.45

Patient identity will be protected through the use of the EHR, as well as by saving abstracted PHI on a password-protected, data-encrypted, secured drive managed by information

technology (IT) at Norwalk Hospital. Additional considerations include the use of REDCap, a secured research platform, for primary data collection and storage. Data will be destroyed when all analyses and publications have been completed.

Risks to patients are negligible as the intervention device is a safe, drug-free, easy to use, and non-invasive. Our exclusion criteria are focused on eliminating any individuals who would be at increased risk of adverse events from using an oPEP device, although such events are very rare. With any airway clearance modality there is the possibility of transient mild bronchospasm and hypoxemia at the initiation of the clearance which improves once the mucus is expectorated. This subtle physiologic phenomenon is typically not clinically evident nor of clinical significance, but this can be ameliorated with coaching by respiratory therapists and investigators who are all trained in the appropriate use of this device, and who are also highly trained to provide immediate care if any clinically evident events occur. The respiratory therapists are very familiar and comfortable with the Aerobika as they are currently using it with patients at Norwalk Hospital for augmentation of secretion clearance, typically in the context of bronchiectasis or COPD exacerbations.

Participation in this study should not result in any additional costs to the patient.

Potential benefits to patients include improved mucociliary clearance, reduction in length of hospitalization, duration of fever, improvement in respiratory symptom-related quality of life and duration of antibiotics, all of which have been shown to be statistically significant in previous studies, although not specific to inpatient treatment of pneumonia, as this study aims to do.

Selection and withdrawal of subjects:

Our inclusion and exclusion criteria are developed based on existing literature, the manufacturer's FDA approval, and the scope of our study.

Inclusion

1. Age 18 years or older
2. Clinical symptoms suggesting pneumonia (eg. cough, fever, pleuritic chest pain, sputum production, dyspnea)
3. Any new chest radiographic infiltrate consistent with pneumonia

Exclusion

1. Untreated or recently (within the past 90 days) treated pneumothorax
2. Active hemoptysis
3. Recent facial, oral, or skull trauma
4. Hemodynamically unstable patients
5. Severe nausea or active vomiting
6. Recent diagnosis of pneumonia prior to current inpatient encounter (within 60 days)
7. Significant cognitive impairment or psychiatric conditions that prevent ability to participate in or cooperate with oPEP use
8. Active tuberculosis or negative pressure isolation for rule out of active tuberculosis
9. Pregnancy
10. Pre-existing medical condition with a life expectancy of less than 3 months
11. Inability to form appropriate mouth seal on device (eg. due to neuromuscular disease)
12. Pre-existing active use of oPEP devices
13. Requiring $\geq 50\%$ FiO₂ or facemask (excluding high flow NC)

Assessment of Efficacy:

This study is not designed to assess the efficacy of any drug, supplement, device, etc.

Assessment of Safety:

No known safety issues exist as no procedures will be conducted on patients for this study outside of the scope of their current use. Furthermore all medical devices in this study are FDA approved and currently being used for the indication being studied in this project.

Statistical Analysis:

Comparative statistics will be employed to determine if outcomes in the intervention (oPEP) group are statistically different from those in the control group. This will be done with the assistance of in-network statisticians as well as available statistical software.

Direct Access to Source Data Documents:

The study's Principal Investigator, primary study coordinator, and co-investigators will have access to all study data. These data will be used for study purposes only, and will be stored on a password-protected, data-encrypted, secure drive managed by IT at Norwalk Hospital. Data may be released to regulatory agencies as necessary, including the US Food and Drug

Administration, Department of Health and Human Services agencies, BRANY, the WCHN IRB, accrediting agencies, and data safety monitoring boards.

References:

2. Diana Tydeman (1989) An investigation into the effectiveness of physiotherapy in the treatment of patients with community-acquired pneumonia, *Physiotherapy Practice*, 5:2, 75-81, DOI: 10.3109/09593988909044416

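### Oxygen need at discharge has no pre-admission reference, so home-oxygen users would be near-fixed events in both arms and blunt a secondary comparison (minor)

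*Combined protocol and SAP*

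**What the plan says.** - **Outcome labels.** Under Objectives, the secondary outcomes include "Reduction in need for oxygen at hospital discharge" and "Reduction in duration of fever". Neither has a definition, a baseline reference or a stated denominator.
- **Eligibility.** Fever is not required for entry; it is one example in a list: "Clinical symptoms suggesting pneumonia (eg. cough, fever, pleuritic chest pain, sputum production, dyspnea"). The only oxygen-related exclusion (number 13) concerns a current requirement of at least 50% "FiO₂ or facemask (excluding high flow NC"). No exclusion names long-term home oxygen.
- **Data collected.** The variable list records "Lung disease (ie. asthma, COPD, ILD, bronchiectasis") as a comorbidity. It includes daily inpatient FiO2 and "Temperature (daily maximum/minimum"). Pre-admission oxygen use is not among the items that can be read. The interview described under Design covers smoking, alcohol, medical and medication histories, and dyspnea, and does not name home oxygen.
- **Analysis.** Under Design: "All analyses will be performed using intention-to-treat as well as a modified intention-to-treat method". The Statistical Analysis section adds only that "Comparative statistics will be employed to determine if outcomes in the intervention (oPEP) group are statistically different from those in the control group".

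**The concern.** A patient already on oxygen at home will normally leave hospital on oxygen. On a yes/no outcome that patient is an event in both arms, whatever the device does. Such events raise both proportions equally, shrink the absolute difference and pull the relative risk towards 1. A real effect on new oxygen need could then be missed. The protocol's background names hypoxemia as a consequence of retained secretions, so the outcome is tied to the proposed mechanism.

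Fever duration raises a related but weaker question. Patients with no fever at entry mostly contribute zeros, and the plan does not say when the count starts. Fever duration is in the hypothesis sentence and is one of the two earlier findings cited as motivation.

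**Working it through.** **1. The plan's own figure.** Inputs from Sample size calculations: means 4.6 and 3.45 days (difference 1.15) and SD 3.16. Two-sided 0.05 and 80% power are not stated and are assumed here.

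n per arm = 2 × (1.960 + 0.842)² × 3.16² / 1.15² = 2 × 7.849 × 9.986 / 1.3225 = 118.5, rounded up to 119.

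This matches the stated 119 per arm (238 in total). It rests on length of stay alone, so no power was planned for oxygen or fever. Below, 119 is simply the number available.

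**2. Oxygen.** Let h be the share on home oxygen and q the rate of new need among the others. All of these are assumptions.

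- Everyone counted: p = h + (1 − h)q in each arm, so the difference is (1 − h)(q1 − q2), with n = 119.
- Non-users only: q1 v q2, with n = 119(1 − h).
- Power (arcsine, two-sided 0.05): with d = 2·asin√p1 − 2·asin√p2, power = Φ(d√(n/2) − 1.96) + Φ(−d√(n/2) − 1.96).

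Example with h = 0.10 and 20% v 8%:

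- Everyone: 0.10 + 0.90 × 0.20 = 0.280 v 0.10 + 0.90 × 0.08 = 0.172. Then d = 0.2599, 0.2599 × √59.5 = 2.005, and power is 51.8%.
- Non-users: n = 107.1, d = 0.3538, 0.3538 × √53.55 = 2.589, and power is 73.5%.

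| Rates in non-users (relative reduction) | h | Relative risk, everyone | Power, everyone | Power, non-users |
|---|---|---|---|---|
| 20% v 8% (60%) | 5% | 0.53 | 63.3% | 75.8% |
| | 10% | 0.61 | 51.8% | 73.5% |
| | 20% | 0.73 | 36.1% | 68.5% |
| 30% v 15% (50%) | 5% | 0.57 | 71.1% | 78.1% |
| | 10% | 0.64 | 62.6% | 75.9% |
| | 20% | 0.73 | 48.1% | 70.9% |
| 20% v 15% (25%) | 5% | 0.80 | 14.5% | 16.8% |
| | 10% | 0.84 | 12.5% | 16.2% |
| | 20% | 0.89 | 10.0% | 14.9% |

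The undiluted relative risks are 0.40, 0.50 and 0.75. The loss runs from 12.5 to 32.4 points in the first block and from 2.3 to 4.9 points in the last. The 25% block uses the relative reduction that the plan adopts for length of stay.

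**3. Fever.** Let f be the share febrile at entry, and k the febrile mean divided by its SD. Suppose afebrile patients contribute exactly zero and the device does nothing for them. The all-patient difference is f times the febrile one, and the all-patient variance is f·SD² + f(1 − f)·mean². The all-patient test statistic as a fraction of the febrile-only one is then 1/√(1 + (1 − f)k²).

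| k | f = 0.3 | f = 0.5 | f = 0.8 |
|---|---|---|---|
| 0.5 | 0.92 | 0.94 | 0.98 |
| 1.0 | 0.77 | 0.82 | 0.91 |
| 1.5 | 0.62 | 0.69 | 0.83 |

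The ratio is below 1 by construction, because the model rules out any effect on fever that begins after entry.

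**The case against.** **The plan is silent; it does not prescribe the dilution.** A reader might infer that the protocol sets a rule counting these patients as failures. It does not. The outcomes are one-line labels, and the intention-to-treat sentence fixes who is analysed, not how oxygen need is defined. This stands, so the point is conditional on a yes/no outcome in everyone randomised, which is the natural reading if nothing is added.

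**The information may be recoverable.** Screening is by chart review, the attending supplies collateral information, and data are abstracted from the record. Home oxygen could be extracted later if it was charted. The variable table also reads as broken, with an empty symptoms cell. So the absence can be claimed only for the readable list, and the documents do not support saying the data would be lost for good.

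**The large power loss reflects the chosen effect.** This stands. At a 25% relative reduction the comparison is badly underpowered either way, and the remedy gains under 5 points.

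**Some chronic-lung patients may already be excluded** through short life expectancy, existing oPEP use or a high oxygen requirement. That is possible, but none of these criteria is aimed at home oxygen.

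**Fever.** A reader might conclude that patients afebrile at entry cannot benefit and should be dropped. They can become febrile later, and the protocol's background lists ongoing fever among the effects of retained secretions. Daily maxima are already collected, and no rule counts fever before randomisation. Replacing the all-randomised analysis would be a trade-off, not a correction.

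**Conclusion.** The point holds for oxygen and is minor. Without a pre-admission reference, home-oxygen users are near-fixed events in both arms and dilute the comparison. Near-fixed is as far as it goes, since a user's flow can change, although a yes/no outcome would not show that.

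Randomisation balances these patients in expectation, so a reader should not infer bias. The primary outcome and the sample size are untouched. Oxygen need is a secondary outcome, was not powered, and is absent from the hypothesis sentence.

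The size is unknown because the documents give neither the home-oxygen share nor the rate of oxygen need. Over assumed shares of 5% to 20%, the loss ranges from about 2 to about 32 power points, and the assumed treatment effect drives most of that range. For fever, the documents support only a clearer definition and a supportive analysis.

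**What to change.** **Oxygen.** Add pre-admission home oxygen (yes/no, and flow if yes) to the baseline interview or the chart abstraction. Define the outcome as new oxygen need at discharge or, for home-oxygen users, a flow above the pre-admission level. Everyone randomised then stays in the analysis. Power will differ somewhat from the non-user column above, depending on how often users' flow rises.

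**Fever.** State a fever threshold and an end point. Count duration from randomisation using the daily maximum temperatures already collected. Keep the all-randomised analysis, and prespecify a supportive one in patients febrile in the 24 hours before randomisation. That subset depends only on pre-allocation status, so the randomised comparison is preserved.

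**Cost.** One added baseline item, two written definitions, and fewer patients in the supportive fever analysis. The sample size does not change.

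### One stated block size of 10, in a trial open to its investigators, could make up to 16.2% of allocations deducible (a ceiling, assuming 5:5 permuted blocks); undisclosed blocks of 8, 10, 12 and 14 are a cheap, optional improvement

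*Combined protocol and SAP*

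**What the plan says.** The Design section of the protocol states that "Patients will then be randomized using block randomization", and then: "We will receive pre-made envelopes in blocks of 10 from a centralized research coordinator". Envelopes are used in sequence: "Once the patient consents to participation, the next consecutively numbered envelope will be opened revealing the allocation". Custody is with one person: "The principal investigator will keep the envelopes secured, and will be responsible for providing each envelope to the enrolling investigator". Concealment before consent is addressed: "Investigators performing the initial screening and enrollment will be blinded to the envelope contents until after the patient consents to participation in the study".

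No within-block ratio, second block size or rule on who may know the size is given.

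Once allocated, arms are visible to the study team. "Patients in the intervention group will be directed to perform the Aerobika therapy twice daily under the guidance of a study investigator" (Design), and no sham is described. Under Direct Access to Source Data Documents, the principal investigator, "primary study coordinator, and co-investigators will have access to all study data".

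**The concern.** Custody of the envelopes and opening only after consent prevent anyone from looking early. They do not prevent deduction. In a balanced block of known length, once one arm is used up, every remaining envelope in that block is known without opening it.

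If someone involved in recruitment could do this, the expected arm might affect, even unintentionally, whom to approach or how a judgement-based criterion is applied. The clearest such criterion is the exclusion for "Significant cognitive impairment or psychiatric conditions that prevent ability to participate in or cooperate with oPEP use" (Selection and withdrawal of subjects), which bears directly on the device. What is at stake is the comparability of the arms, in a trial whose staff know the arms once envelopes are opened.

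**Working it through.** **Inputs.** Block size 10 (Design; read here as the permuted block). Total 238, as 119 + 119 (Sample size calculations). Ratio 5:5 within blocks is assumed; it fits the equal arms but is not stated.

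**The plan's own figure.** The protocol gives no predictability figure, so the only one to reproduce is N. With means 4.6 and 3.45 days, SD 3.16, and two-sided 5% and 80% power (neither is stated), n = 2(1.960 + 0.842)² × 3.16² / 1.15² = 118.5, so 119 per group. It matches. N matters here only because 238 is 23 blocks of 10 plus 8.

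**Ceiling: everything known.** Position k of a 5:5 block is certain if one arm is exhausted in the first k − 1:

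P(k) = 2·C(5, k−6) / C(10, k−1), for k = 6 to 10

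| Position | 6 | 7 | 8 | 9 | 10 |
|---|---|---|---|---|---|
| P(certain) | 0.0079 | 0.0476 | 0.1667 | 0.4444 | 1.0000 |

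The sum is 1.667 per full block. The last 8 positions add 0.0079 + 0.0476 + 0.1667 = 0.222. Total: 23 × 1.667 + 0.222 = 38.6 of 238, or 16.2%. Of these, 23 (60%) are tenth envelopes; ninth and tenth together are 23 × 1.4444 = 33.2 (86%).

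**Incomplete tracking.** Let each earlier allocation be known independently with probability p, block starts still known. Certainty needs all five allocations of the exhausted arm to be known, so the ceiling is multiplied by p⁵.

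| p | p⁵ | Certain allocations | Share of 238 |
|---|---|---|---|
| 1 | 1 | 38.6 | 16.2% |
| 0.90 | 0.590 | 22.8 | 9.6% |
| 0.75 | 0.237 | 9.1 | 3.8% |
| 0.50 | 0.031 | 1.2 | 0.5% |

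**Varying blocks.** Trials of 238 were simulated with sizes drawn at random, against an observer who sees every allocation, knows the set of sizes and updates by Bayes' rule. This observer is harder to defeat than one from whom the sizes are withheld.

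| Block sizes | Certain | Predictable at ≥90% | Predictable at ≥80% | Best guess correct |
|---|---|---|---|---|
| 10 only | 16.2% | 16.2% | 18.7% | 65.1% |
| 8, 10, 12, 14 | 0.7% | 1.7% | 8.5% | 64.6% |
| 4, 6, 8 | about 2.2% | – | about 25% | 68.0% |

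The mix matters. Other mixes left certain shares of 5.4% (4, 6), 7.6% (4, 8), 3.1% (8, 10) and 1.5% (6, 8, 10). An observer who does not know the set, and allows for a size larger than any used, is never certain.

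**Balance at N = 238 (exact).** Fixed 10: difference 0 in 55.6% of trials, 2 in 44.4%. With 8, 10, 12, 14: 0 in 58.8%, 2 in 38.2%, 4 in 3.0%, 6 in 0.05%. Six is the maximum, since 238 and all blocks are even and the largest half-block is 7. The worst split, 122/116, has efficiency 4 × 122 × 116 / 238² = 56,608 / 56,644 = 99.9% of 119/119.

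**The case against.** The other side has a strong case, and much of it stands as a limit on the point.

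- The sentence is ambiguous. Blocks of 10 may describe how envelopes are delivered, not the permuted block. The block size is then unstated and 16.2% does not follow. That is no reassurance: smaller fixed balanced blocks are more deducible (25% per complete block at size 6, 33% at size 4). It does make the figure conditional.
- The observer behind 16.2% is not placed at the enrollment decision. Only the principal investigator clearly handles every envelope and can see all data, and the protocol does not say that this person enrolls. Co-investigators also have data access, but nothing says that anyone tracks the sequence.
- Room to act is small. Screening uses listed ICD-10 codes, the attending must give permission, and most exclusions are factual.
- Expectation does not require certainty, and best-guess accuracy is nearly the same after the change.

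A reader might infer that concealment has failed, that a sixth of allocations will in fact be foreseen, or that length of stay will be biased. The documents support none of these. They provide central preparation, sequential numbering, custody and opening after consent, and they give no evidence of tracking or selective enrollment. What remains is narrower: those safeguards do not address inference from earlier allocations.

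**Conclusion.** The point holds as an optional, cheap improvement to allocation concealment. Fixed blocks of 10 are neither an error nor a contradiction in the plan.

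The size is a ceiling of 16.2% (38.6 of 238). It rests on four assumptions: 10 is the permuted block, blocks are 5:5, every earlier allocation is known, and block starts are known. With half of the earlier allocations known, it is 0.5%.

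A reader might also infer that any varying-block scheme brings certainty down to 0.7%, or makes the sequence unpredictable. Neither is so. The 0.7% belongs to the mix 8, 10, 12, 14; the other mixes listed above, whose sizes the observer knows, leave between 1.5% and 7.6%. Mixes of small sizes can also raise the share predictable at 80% or more. The benefit is the removal of near-certain predictions, not of guessing in general.

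**What to change.** Have the central coordinator, who already supplies the envelopes, generate the list with block sizes of 8, 10, 12 and 14 in random order, not disclosed to investigators. Avoid small sizes such as 4 and 6. Deliver envelopes in numbered batches whose ends do not match block ends, and keep the list outside the study data that investigators can open.

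In the Design section, replace the words on blocks of 10 with: *in numbered batches; block sizes vary and are held by the central coordinator*. This also settles whether 10 meant a batch or a block.

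The cost is a new envelope list, one changed sentence and slightly looser balance: a final difference of at most 6 patients, with negligible loss of efficiency. Sample size, eligibility and treatment are unaffected.
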